5. AMENDMENTS AND UPDATES

Version Identifier	Date	Amendment Type (substantial or administrative)	Protocol Section(s) Changed	Summary of Amendment(s)	Reason
2.0	15 September 2025	Substantial	6. Milestones	Update milestones, interim report was removed and replaced with interim analysis	Reflective of revised project deliverables
2.0	15 September 2025	Substantial	9. Research Methods 
 • 9.1. Study Design • 9.2. Setting • 9.3. Variables • 9.7. Data analysis 	- Additional assessment periods for adverse events (Obj. 5) and supportive medication assessment (Exploratory Obj. 1) - Clarified definitions of existing variables with additional data information - Added new variables of interest for Objective 2 (i.e., addition of variables of interest at a patient and claim level), and Objective 5 (i.e., concomitant medication at the same time as the AE event).	- Enhance data granularity following clinical input. - Improvement of consistency with data - Capture additional data relevant to the study objectives
2.0	15 September 2025	Substantial	9.7.5. Subgroup analysis	A subgroup analysis was added for low weight patients receiving elranatamab.	Provide deeper insights into treatment outcomes and safety within this specific patient population,

090177e1a4a71ff1\Approved\Approved On: 05-Nov-2025 14:15 (GMT)

6. MILESTONES

Milestone	Planned Date
Start of data collection	15 July 2025
End of data collection	30 June 2026
Interim analysis	30 September 2025
Registration in the HMA-EMA Catalogues of RWD studies	15 July 2025
Final study report	30 November 2026

090177e1a4a71ff1\Approved\Approved On: 05-Nov-2025 14:15 (GMT)

7. RATIONALE AND BACKGROUND

Multiple myeloma (MM) is a hematologic malignancy characterized by an excess of monoclonal bone marrow (BM) plasma cells. In Japan, it is estimated that MM has an incidence rate of 5.8 cases and a death rate per capita of 3.5 per 100,000 people (1). Though its incidence has increased over recent years, the mortality rates have decreased – coinciding with the introduction of novel therapies (2). Historically, treatment options for patients with MM were limited to a combination of alkylating agents, such as melphalan, and steroids such as prednisone (3,4). However, the development of new therapies has led to profound changes in the treatment landscape and has increased overall survival (OS) in patients with MM especially with the approval of therapies designed to target specific pathogenic pathways, including the following: proteasome inhibitors (PIs) (carfilzomib, ixazomib, and bortezomib), immunomodulatory imide drugs (IMiDs) (pomalidomide, thalidomide, and lenalidomide), and anti-CD38 monoclonal antibodies (anti-CD38) (daratumumab, daratumumab and hyaluronidase-fihj, and isatuximab-ifrc) (5).

Despite treatment advancements, many MM patients experience relapse or refractory disease (RRMM), leading to poor prognosis and limited options. Elranatamab is the first bispecific B-cell maturation antigen (BCMA)-directed monoclonal antibody to receive approval from the Japanese Pharmaceuticals and Medical Devices Agency (PMDA) in March 2024. Elranatamab was approved for the treatment of patients with RRMM who have been exposed to at least three standard therapies including IMiD, PI, and anti-CD38, i.e., triple-class exposed (TCE).

Results from MagnetisMM-2 and MagnetisMM-3 reported common adverse events (AE) to be CRS, ICANS, cytopenia, and infections (6,7). A past study sponsored by Pfizer compared Japanese patients in MagnetisMM-2 and MagnetisMM-3 trials to the entire trial cohort and found no new safety signals and similar overall response rates (8). Some real-world (RW) studies have shown that other MM treatments, such as thalidomide and bortezomib, have differing RW safety profiles between Western and Japanese or other East Asian populations (9–12). Other Pfizer-sponsored studies are being conducted that assess AE with elranatamab using real-world data (RWD), but these studies are all US-based and, thus far, similar RW evidence has not been generated in Japan.

As the first BCMA-directed bispecific monoclonal antibody approved in Japan, elranatamab represents a new addition to the treatment landscape for RRMM in Japan. This study aims to describe its RW use in clinical practice, including patterns of patient selection, treatment administration, and adverse event management in the post-approval setting. Utilizing a Japanese hospital-based administrative health dataset, which covers approximately 26% of all hospitals in Japan and includes over 40 million patient records, this study will describe the RW administration of elranatamab in patients with MM.

This noninterventional study is designated as a Post-Authorization Safety Study (PASS) and is conducted voluntarily by Pfizer.

8. RESEARCH QUESTIONS AND OBJECTIVES

Research Question: What are the characteristics of adult patients with MM who initiate elranatamab in Japan, and the SUD process, treatment patterns, HCRU, and safety associated with elranatamab administration?

The following objectives will be assessed among patients with MM receiving elranatamab:

Primary objectives:

- Objective 1: To describe patients with MM initiating elranatamab, including demographics, treatment and medical history.
- Objective 2: To describe and characterize elranatamab utilization, including timing, administration and dosing, during the follow-up period, including the step-up dosing (SUD) period.

Secondary objectives:

- Objective 3: To describe HCRU and costs associated with elranatamab usage during the follow-up period, including the SUD period.
- Objective 4: To describe the use of other treatments for MM including supportive therapy during the follow-up period.
- Objective 5: To describe incidence and prevalence of cytokine release syndrome (CRS), immune effector cell associated neurotoxicity syndrome (ICANS), and cytopenias during the SUD period.
- Objective 6: To describe infection incidence and prevalence during the follow-up period.

Exploratory objectives:

- Exploratory Objective 1: To describe the use of supportive medications during the SUD period and administration of IVIG within the 30-day post-index period.

9. RESEARCH METHODS

9.1. Study Design

This retrospective cohort study will assess the demographics, clinical history, SUD process, HCRU, and safety of elranatamab in MM patients with an elranatamab hospital claim. De-identified data from the Japan Medical Data Vision (MDV) will be used.

[figure not shown]
A retrospective cohort design was chosen because it allows for efficient use of existing RW data to evaluate treatment patterns and outcomes in a newly approved therapy, without the need for prospective data collection. This design is well-suited for descriptive analyses and enables timely insights into the early use of elranatamab in a RW setting.

The primary endpoints include patient demographics, clinical characteristics, and treatment patterns. Secondary endpoints include HCRU and safety outcomes. No formal measures of effect will be calculated. All analysis will be descriptive, with no a priori hypotheses or statistical comparisons between exposure groups.

The study population will be comprised of individuals aged 18 and older who initiated elranatamab between March 26, 2024, the PMDA approval date for elranatamab, and the end of data availability. The study period will be from the start of data availability, April 2008, to the end of data availability in MDV. The study period will remain the same for all study objectives. The patient baseline period will be from MM diagnosis to the start of the index treatment. The patient index date will be determined as the date of first hospital claim with an administration of elranatamab. The follow-up period will be defined as the period between the index date and the end of the hospital claim of the last elranatamab administration

inclusive. The SUD period will be defined as the period between the date of the first 44mg/1.1mL vial and the first 76mg/1.9mL vial of elranatamab, see more details in Section 9.2 and 9.3.1. Figure 1

Figure 1. Study design

Abbreviations: CCI: Charlson Comorbidity Index; HCRU: Health Care Resource Utilization; MM: multiple myeloma; SUD: Step-up dosing;

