SUD period: defined as the period between a patient's first 44mg/1.1mL vial of elranatamab and first 76mg/1.9mL vial of elranatamab, inclusive. See Section 9.3.1 and Annex 1 for more details. Within the SUD period, three sub-periods are identified:

- **Overall:** defined as the period between first 44mg/1.1mL vial and first 76mg/1.9mL vial of elranatamab.
- **First 44mg/1.1mL vial – Second 44mg/1.1mL vial:** defined as the period between the two 44mg/1.1mL vials of elranatamab, if second 44mg/1.1mL vial is administered.
- **Second 44mg/1.1mL vial – first 76mg/1.9mL vial:** defined as the period between the second 44mg/1.1mL vial and the first 76mg/1.9mL vial of elranatamab, if second 44mg/1.1mL vial is administered.

Follow-up period: defined as the period between the first hospital claim for elranatamab (index date) and the end of the hospital claim of the last elranatamab administration. Within this follow-up period, five sub-periods are identified (when sufficient follow-up time is available at the patient level). These sub-periods allow for reporting study endpoints across different phases of the follow-up period, and are based on expected dosing administrations and schedule of patients with switch to bi-weekly administrations from label guidance (see [Table 10. Dosing Schedule of Elranatamab during Follow-up Period for Patients Switching to](#)

[Q2W](#) and [Table 11. Dosing Schedule of Elranatamab during Follow-up Period for Patients staying on QW](#)):

- **Index date to day 8:** defined as the first 8 days post-index date, inclusive. Also defined as day 1 to day 8.
- **Day 9 to day 168:** defined as the period from day 9 to day 168 post-index date.
- **Day 169+:** defined as the period from day 169 post-index date to end of follow-up period.

- **Overall follow-up:** defined as the period from index date to end of follow-up period.

IVIG follow-up assessment period: defined as the 30-day window post index date. If a patient has fewer than 30 days of data available post to the index date, the assessment window will be equal to the maximum number of days available post to the index date.

CRS/ICANS follow-up assessment period: defined as the 14-day window post index date. If a patient has fewer than 14 days of data available post to the index date, the assessment window will be equal to the maximum number of days available post to the index date.

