9.2.1. Inclusion Criteria

Patients must meet all of the following inclusion criteria to be eligible for inclusion in the study:

1. First hospital health claim with an administration of elranatamab on or after March 26, 2024.
2. Have a diagnosis of MM.
3. Aged ≥ 18 years at the time of first hospital claim for elranatamab (i.e., index date).

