9.3.1 Exposure Groups and Assessment Periods

[Table 1](#) outlines the variables to define exposure groups that will be used to identify patients and stratify analyses.

Table 1. Variables for Exposure

Variable	Role	Data Source	Operational Definition	
			Definition	Assessment Period(s)
Study population	Exposure	MDV	All patients with MM who have a hospital claim for elranatamab after March 26, 2024, and who meet the inclusion and exclusion criteria outlined in Sections 9.2.1 and 9.2.2.	Index date
SUD Exposure Group	Exposure	MDV	
Group A: Complete and timely SUD period
 
Patients in the study population with two 44mg/1.1mL vials (second 44mg/1.1mL vial is received 1 to 7 days after the first) and one subsequent 76mg/1.9mL vial between 1 to 7 days after second 44mg/1.1mL vial
 
Group B: Complete but not timely SUD period
 
Patients in the study population with two 44mg/1.1mL vials and one subsequent 76mg/1.9mL vial after the second 44mg/1.1mL vial, with one or both intervals between doses ranging from 8 to 14 days.
 
Group C: Alternative SUD period
 
 • Only one 44mg/1.1mL vial: patients in the study population with only one 44mg/1.1mL vial prior to receiving a 76mg/1.9mL vial • More than two 44mg/1.1mL vials: patients in the study population with more than 	SUD period

090177e1a4a71ff1\Approved\Approved On: 05-Nov-2025 14:15 (GMT)

Variable	Role	Data Source	Operational Definition	
			Definition	Assessment Period(s)
			
two 44mg/1.1mL vials prior to receiving a 76mg/1.9mL vial
 
 Extremely untimely: patients in the study population with more than 14 days between the first and second 44mg/1.1mL vial or between the second 44mg/1.1mL vial and the first 76mg/1.9mL vial 
Note that patients who received only 44mg/1.1mL vials or only 76mg/1.9mL vials are not classified under any SUD exposure group but will remain part of the study population.
	

Figure 2 illustrates possible elranatamab administration scenarios for each SUD group. These examples are not exhaustive and do not represent all potential administration schedules.

090177e1a4a71ff1\Approved\Approved On: 05-Nov-2025 14:15 (GMT)

Figure 2. SUD Periods Administration Schedule

[figure not shown]

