Duration of treatment, patient level	Outcome	MDV	Days between first and last treatment administration for elranatamab (continuous)	Follow-up period
Duration of treatment, claim level	Outcome	MDV	Total calendar duration of elranatamb observation in days, and the date of the first observed elrantatamab claim	Follow-up period
Only 44mg/1.1mL vials [Summary statistic]	Outcome	MDV	Number of patients with only 44mg/1.1mL vials during the time period (yes/no)	Follow-up period
Only 76mg/1.9mL vials [Summary statistic]	Outcome	MDV	Number of patients with only 76mg/1.9mL vials during the time period (yes/no)	Follow-up period
Relative Administration Intensity (RAI) [Summary statistic]	Outcome	MDV	Ratio of the elranatamab administrations received divided by the expected number of administrations according to the Japan elranatamab label See Section 9.7.4 for more details	Follow-up period

Abbreviations: mL: millilitre; mg: milligram; RAI: Relative Administration Intensity; SUD: step-up dosing.

Table 5. Variables for Outcomes (Objective 3 – HCRU and Costs)

090177e1a4a71ff1\Approved\Approved On: 05-Nov-2025 14:15 (GMT)

Variable	Role	Data Source	Operational Definition	
			Definition	Assessment Period(s)
IP claim [Summary statistic]	Outcome	MDV	Number of patients with ≥ 1 all-cause IP claim (yes/no)	HCRU baseline period SUD period Follow-up period (overall only)
			Number of all-cause IP claims PPPM. Reported for all patients and for patients with ≥ 1 all-cause IP claim.	HCRU baseline period Follow-up period (overall only)
			Number of all-cause IP claims PPPD. Reported for all patients and for patients with ≥ 1 all-cause IP claim.	SUD period
OP claim [Summary statistic]	Outcome	MDV	Number of patients with ≥ 1 all-cause OP claim (yes/no)	HCRU baseline period SUD period Follow-up period (overall only)
			Number of all-cause OP claims PPPM. Reported for all patients and for patients with ≥ 1 all-cause OP claim.	HCRU baseline period Follow-up period (overall only)
			Number of all-cause OP claims PPPD. Reported for all patients and for patients with ≥ 1 all-cause OP claim.	SUD period

090177e1a4a71ff1\Approved\Approved On: 05-Nov-2025 14:15 (GMT)

Variable	Role	Data Source	Operational Definition	
			Definition	Assessment Period(s)
ED claim [Summary statistic]	Outcome	MDV	Number of patients with ≥ 1 all-cause ED claim (yes/no)	HCRU baseline period SUD period Follow-up period (overall only)

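### With no minimum observation after index, patients cut off mid-step-up are counted with those who stopped on 44mg vials, and some CRS/ICANS and IVIG windows are only partly observed

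*Protocol*

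**What the plan says.** **Entry.** Section 9.1 takes patients who start "between March 26, 2024, the PMDA approval date for elranatamab, and the end of data availability". The first criterion in section 9.2.1 is "First hospital health claim with an administration of elranatamab on or after March 26, 2024"; the other two concern the myeloma diagnosis and age. The single exclusion in 9.2.2 concerns clinical trials. None sets a minimum time after index.

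**Step-up groups.** In section 9.3.1, Table 1, Groups A, B and C all need a 76mg vial. Patients with only 44mg vials are "not classified under any SUD exposure group but will remain part of the study population".

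**Only-44mg endpoint.** Table 4 (Objective 2, a primary objective) defines it as "Number of patients with only 44mg/1.1mL vials during the time period (yes/no". No observation time is required, and Table 2 reports follow-up endpoints of this objective in the whole study population.

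**Windows.** Section 9.2 says for CRS and ICANS: "If a patient has fewer than 14 days of data available post to the index date, the assessment window will be equal to" the days that exist. The 30-day IVIG window has the same rule: "If a patient has fewer than 30 days of data available post to the index date, the assessment window will be equal to" the days that exist. Tables 7 and 9 record these events as yes/no, and section 9.7.2 divides incidence by a count of patients at risk. Table 2 reports CRS/ICANS and 30-day IVIG only in Groups A, A+B and C.

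Section 9.7.6 plans no sensitivity analysis. Section 9.9 mentions data lags but not truncation at the cut.

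**The concern.** A patient whose first vial falls a few days before the cut cannot yet have a 76mg claim. Under these rules that patient is recorded exactly like one who stopped during step-up. The reader of a primary-objective table cannot separate the two.

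Two smaller effects follow. A step-up that starts near the cut is more likely to be seen complete if it is fast, so Groups A to C and the times to the first 76mg vial lean towards fast completers. And a grouped patient whose data end before day 14 or day 30 contributes a full unit to the denominator but only part of the window to the numerator, which pulls those proportions down.

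**Working it through.** The protocol gives no figure of its own to reproduce, so the size is worked out from its dates and windows.

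**Inputs from the protocol**
- Entry opens 26 March 2024 (9.1).
- 128 patients at the February 2025 cut (9.5). The day is not stated; 1 and 28 February give T = 313 or 340 days, counting both ends.
- Data collection ends 30 June 2026 (section 6), so T = 827 if the data run to that day.
- Days from index to first 76mg vial (Table 1): Group A 1+1 = 2 to 7+7 = 14; Group B 8+1 = 9 to 14+14 = 28; Group C extremely untimely from 15+1 = 16, with no upper limit.

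**Assumptions**
- Accrual is uniform, or rises linearly from zero.
- Step-up takes L = 7 days (Tables 10 and 11 expect three administrations by day 8) or 14 days (the upper end of Group A).

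**Step 1. Share starting in the last w days.** Uniform: w/T. Rising: 1 − (1 − w/T)².

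| w | Feb 2025, uniform | Feb 2025, rising | 30 June 2026, uniform to rising |
|---|---|---|---|
| 7 | 2.1–2.2% (2.6–2.9 of 128) | 4.1–4.4% (5.2–5.7) | 0.8–1.7% |
| 14 | 4.1–4.5% (5.3–5.7) | 8.1–8.7% (10.3–11.2) | 1.7–3.4% |
| 30 | 8.8–9.6% (11.3–12.3) | 16.9–18.3% (21.6–23.4) | 3.6–7.1% |

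**Step 2. 44mg-only because of the cut.** These are the starters in the last L days. At L = 7: 128 × 7/340 = 2.6 to 128 × 7/313 = 2.9. At L = 14: 5.3 to 5.7. By June 2026 the uniform shares are 7/827 = 0.8% and 14/827 = 1.7%. The interim analysis is dated 30 September 2025; its cut is not given, but a cut on that day (T = 554) would give 7/554 = 1.3% and 14/554 = 2.5%.

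**Step 3. Grouped patients with a shortened window.** These start between L days and the window length before the cut.
- L = 7, CRS/ICANS: 14 − 7 = 7 start dates, 2.6 to 2.9 patients.
- L = 7, IVIG: 30 − 7 = 23 start dates, 128 × 23/340 = 8.7 to 128 × 23/313 = 9.4 patients; by June 2026, 23/827 = 2.8%.
- L = 14: none for CRS/ICANS; 16 start dates, 6.0 to 6.5 patients, for IVIG.

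If all other patients are grouped (about 125), the shortened share at L = 7 is about 2% for CRS/ICANS and 7 to 8% for IVIG. The bias must be smaller than this, because the observed part of each window still counts.

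**Step 4. Selective loss.** Among starters in the last W days, the share with a complete step-up is (W − L)/W.

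| L (days) | W = 30 | W = 340 |
|---|---|---|
| 7 | 77% | 97.9% |
| 14 | 53% | 95.9% |
| 21 | 30% | 93.8% |
| 28 | 7% | 91.8% |

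To see what this does to the group mix, assume a true mix of 70% A, 20% B and 10% C-untimely, with mean step-up lengths of 8, 18.5 and 29 days. The fractions seen over 340 days are 0.70 × (1 − 8/340) = 0.6835, 0.20 × (1 − 18.5/340) = 0.1891 and 0.10 × (1 − 29/340) = 0.0915. They sum to 0.9641, so the observed mix is 70.9/19.6/9.5.

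**The case against.** Several points on the other side stand.

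- The study is descriptive. The only-44mg endpoint is a count of claims seen, is nowhere called non-completion, and section 9.2 allows a 44mg vial to be a partial dose. The count is not false; it is hard to interpret.
- The window shortening is openly stated, and the baseline windows use the same rule. What remains is that a shortened window is then analysed as a complete yes/no.
- The February 2025 cut is only indicative of sample size; the report will use the most recent cut, where the effect is diluted.
- The SAP could list incomplete windows. But the entry rule, the groups, the endpoint and the shortening are all fixed in the protocol, which section 9.8 says will be strictly followed.

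Three stronger readings are tempting and are not supported.

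- A reader might infer that late starters still on 44mg vials are counted as free of CRS, ICANS and 30-day IVIG. They are not: Table 2 limits those endpoints to groups that require a 76mg vial. Such a patient could count as an IVIG No only under Objective 4.
- A reader might infer that the timely share is materially overstated. In the illustration it moves from 70% to 70.9%.
- A reader might express the excess as a large relative inflation of the only-44mg count. That needs a true non-completion rate, which the protocol does not give. With an assumed 3 to 5% (4 to 6 of 128), the range is 2.6/6 = 43% to 5.3/4 = 132% at February 2025. At June 2026 (128 × 827/340 = 311 patients, 9.3 to 15.6 non-completers) it is about 17 to 56%. This is too dependent on assumption to carry the point.

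**Conclusion.** The point holds at a modest size. A few patients in a primary-objective count will be there only because the data ended, and the plan gives no way to tell them apart. The downward bias in grouped CRS/ICANS and IVIG proportions is slight, and the selective loss of slow step-ups matters mainly for the smaller Groups B and C. The effect is largest at early cuts such as the interim analysis, and section 12 plans external dissemination of interim results.

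The figures rest on the assumed accrual shape and step-up length. With uniform accrual and a 7-day step-up, about 3 of 128 patients are affected in the only-44mg count. Linearly rising accrual roughly doubles the shares. Under uniform accrual to 30 June 2026 they fall to about 1 to 2% for 44mg-only and under 4% for IVIG. The change is worth making because it is cheap, not because the results would otherwise be badly wrong.

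**What to change.** In sections 9.2 and 9.2.1, define an analysis set for step-up group assignment, the only-44mg count, CRS/ICANS and 30-day IVIG: patients whose index date is at least 30 days before the data cut. Let this restriction replace the shortening of the post-index windows at the cut. Keep later starters in Objective 1, and report how many were set aside.

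Apply the rule by calendar date only, with no exception for death. Keeping late starters who died while dropping those who survived would select on outcome. Patients indexed early enough who die or leave the hospital within 30 days stay in.

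Thirty days covers the longest Group B step-up (28 days) and both windows. The cost is a sentence or two, a date filter, and about 11 to 12 patients at the February 2025 cut (22 to 23 if accrual rises). With a 7-day step-up, those 11 to 12 are the roughly 3 still in step-up plus the roughly 9 with an unfinished IVIG window; some had complete CRS/ICANS windows and are lost from that table too. Group C step-ups longer than 30 days can still be missed, which section 9.9 should say.
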